11. MEASUREMENT OF EFFECT

11.1 Antitumor Effect

All patients will have a baseline PET/CT scan within 6 weeks prior to the start of therapy. For the purposes of this study, patients should be re-evaluated for response by PET/CT scans every 8 weeks. In addition, a bone marrow aspirate and biopsy are required within 6 weeks before the 1st treatment for all patients. If the initial marrow shows involvement, repeat marrow is required to confirm a CR. If the initial marrow is negative, further bone marrow biopsy is not required. The marrow should be sent for aspirate, core pathology, flow cytometry, and cytogenetics.

Response and progression will be evaluated in this study using the International Harmonization Project for lymphoma criteria.¹⁰⁴

11.1.1 Definitions

Evaluable for toxicity. All patients will be evaluable for toxicity from the time of their first treatment with AT13387 (onalespib).

Evaluable for objective response. Only those patients who have measurable disease present at baseline, have received at least one cycle of therapy, and have had their disease re-evaluated will be considered evaluable for response. These patients will have their response classified according to the definitions stated below.

11.1.2 Response Criteria

11.1.2.1 Evaluation of Disease

Complete Response (CR): Disappearance of all evidence of disease. For FDG-avid or PET positive sites of disease prior to therapy, a mass of any size is permitted if PET negative; for variably FDG avid or PET negative lesions, regression to normal size on CT is necessary. The spleen or liver must also be nonpalpable with disappearance of any nodules, and the bone marrow, if initially involved, must be cleared on repeat biopsy.

Partial Response (PR): Regression of measurable disease and no new sites of disease. This is defined as a $\geq 50\%$ decrease in the sum of the diameters of the up to 6 largest dominant masses with no increase in size of other masses. If the sites of disease were

PET positive at baseline, there must be at least one previously involved site that remains PET positive. For disease involving the spleen or liver, there must be a $\geq 50\%$ decrease in the sum of the diameters of nodules (of if a single nodule, $\geq 50\%$ reduction in its greatest transverse diameter) and/or no increase in size of the liver or spleen.

Progressive Disease (PD): Any new lesion or an increase by $\geq 50\%$ of previously involved sites from nadir. This includes the appearance of any new lesion(s) $> 1.5\text{cm}$ in any axis, a $\geq 50\%$ increase in the sum of diameters of > 1 site of disease or $\geq 50\%$ increase in the longest diameter of a previously identified node $> 1\text{cm}$ in short axis. If the sites of disease were PET positive at baseline, they must remain PET positive.

Stable Disease (SD): Neither sufficient shrinkage to qualify for PR nor sufficient increase to qualify for PD. If sites of disease were FDG avid or PET positive prior to therapy, they remain PET positive with no new sites of disease. If sites of disease were variably FDG avid or PET negative, there has been no change in the size of previous lesions.

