	APPENDIX I EXAMPLE OPHTHALMOLOGIC EXAMINATION WORKSHEET	

1. OBJECTIVES

1.1 Primary Objectives

- 1.1.1 Overall response rate (ORR) to single agent AT13387 (onalespib) as measured by the proportion of partial and complete responses (PR + CR) in patients with relapsed/refractory ALK+ anaplastic large cell lymphoma (ALCL), mantle cell lymphoma (MCL), and BCL6+ diffuse large B cell lymphoma (DLBCL).

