d: Cycle 2 and on, electrocardiograms (EKGs) will be done on day 1 of each cycle. EKGs should be done per standard of care at the treating institution. EKGs are not required to be in triplicate, but if there is an issue with a QTc value on the single EKG, an average QTc is acceptable on three triplicate EKGs if it makes a patient eligible for treatment.
e: Adverse event and concomitant medication evaluation will be assessed at each visit by the clinical trial personnel.
f: If bone marrow biopsy is negative at screening, it does not need to be repeated. If the bone marrow biopsy is involved at baseline, it must be repeated in order to confirm a complete response (CR).
g: To be collected in 1 x 4 mL purple top EDTA tube. However, a minimum of 1 mL of blood is needed so any tube size that meets this 1 mL minimum is acceptable. This can be shipped along with the frozen tissue.
h: Serum pregnancy test (women of childbearing potential).
i: Off-treatment evaluation. Patients who come off treatment for progression will have telephone follow-up every 6 months for up to 1 year

- | |
|--|
| 
for OS endpoints. Patients who come off treatment for reasons other than progression will have CT scans (see below) at 6 and 12 months, or until the time of progression or next therapy, for PFS and DOR endpoints.
 
j: CT scans will be repeated at 6 and 12 months, or until the time of progression, for patients who come off study for reasons other than disease progression.
 
k: Biopsy or sample of most accessible tissue, which may be bone marrow, body fluid, lymph node, or other tumor site. The sample should be from the same tumor source (ie body fluid, bone marrow, lymph node, or other tumor site) at each timepoint. This is distinct from the bone marrow biopsy required at screening for lymphoma staging. However, if the bone marrow is involved at screening, this can be used as the site of tumor biopsy for patients during pre-treatment, cycle 1 and at the time of progression. Biopsies during cycle 1 should optimally be done on day 17, but can be done between days 17-22.
 |
|--|

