13.5.2 Evaluation of Response

All patients included in the study must be assessed for response to treatment, even if there are major protocol treatment deviations or if they are ineligible. Each patient will be assigned one of the following categories: 1) complete response, 2) partial response, 3) stable disease, 4) progressive disease, 5) early death from malignant disease, 6) early death from toxicity, 7) early death because of other cause, or 9) unknown (not assessable, insufficient data). [Note: By arbitrary convention, category 9 usually designates the “unknown” status of any type of data in a clinical database.]

All of the patients who met the eligibility criteria (with the possible exception of those who received no study medication) should be included in the main analysis of the response rate. Patients in response categories 4-9 should be considered to have a treatment failure (disease progression). Thus, an incorrect treatment schedule or drug administration does not result in exclusion from the analysis of the response rate. Precise definitions for categories 4-9 will be protocol specific.

All conclusions should be based on all eligible patients. Sub-analyses may then be performed on the basis of a subset of patients, excluding those for whom major protocol deviations have been identified (*e.g.*, early death due to other reasons, early discontinuation of treatment, major protocol violations, etc.). However, these subanalyses may not serve as the basis for drawing conclusions concerning treatment efficacy, and the reasons for excluding patients from the analysis should be clearly reported. The 95% confidence intervals should also be provided.

REFERENCES

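### As worded, PR can leave a patient with no response category: PET cleared everywhere, at least 50% shrinkage, but spleen/liver still palpable or baseline-PET-positive marrow still involved

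*Combined protocol and SAP*

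**What the plan says.** The primary endpoint (Section 1.1) is the proportion of patients with PR or CR. Section 11.1.2.1 defines the categories.

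- **CR.** A residual mass of any size is allowed if a previously PET-positive site is now PET negative. Two further conditions apply: "The spleen or liver must also be nonpalpable with disappearance of any nodules", and "bone marrow, if initially involved, must be cleared on repeat biopsy".
- **PR.** At least 50% decrease in the summed diameters, no growth elsewhere, no new site, and a spleen/liver condition. For sites that were "PET positive at baseline, there must be at least one previously involved site that remains PET positive".
- **SD.** Shrinkage short of PR and growth short of PD. In addition, "If sites of disease were FDG avid or PET positive prior to therapy, they remain PET positive with no new sites of disease".
- **PD.** Any new lesion, or at least 50% increase from nadir. It closes with "If the sites of disease were PET positive at baseline, they must remain PET positive".

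Section 11.1 says response will be evaluated by the cited International Harmonization Project criteria. Section 11.1.1 says evaluable patients are classified by the definitions that follow it in the text. No order of precedence is given.

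Section 13.5.2 assigns every patient to CR, PR, SD, PD, one of three early-death categories, or 9 (unknown, glossed as not assessable or insufficient data). It adds: "Patients in response categories 4-9 should be considered to have a treatment failure (disease progression".

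**The concern.** The four definitions should cover every assessed patient, and a better result should never move a patient out of the responder group. The PET sentence in PR breaks both rules. It describes what usually separates PR from CR, residual uptake, but is written as a requirement for PR. CR can also fail for reasons other than uptake (a palpable organ, or marrow on biopsy), and a patient who fails only on those has no uptake left to satisfy PR.

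Such a patient is lost from ORR unless another scan qualified as PR or CR under the best-response rule in Section 11.1.2.2. MCL and DLBCL each stop at 0 responses in 10 and succeed at 3 in 20. ALCL needs 3 in 10. With thresholds this low, one patient can decide a cohort.

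**Working it through.** **Step 1: apply the definitions.** Take a patient PET positive at baseline, with at least 50% shrinkage, no growth and no new lesion.

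| PET now | Marrow (if initially involved) | Spleen/liver | Literal category |
|---|---|---|---|
| Negative | Cleared | Not palpable | CR |
| One site positive | Cleared | Not palpable | PR |
| One site positive | Still involved | Not palpable | PR |
| Negative | Still involved (PET positive at baseline) | Not palpable | None |
| Negative | Cleared | Palpable | None |

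In the last two rows:
- CR fails on the marrow or organ clause.
- PR fails because no site remains PET positive.
- SD fails because shrinkage reaches the PR level and the sites are no longer PET positive.
- PD fails because there is no growth and no new lesion.

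Rows 3 and 4 differ only in that the last PET-positive site has cleared, and that improvement removes the patient from PR.

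**Step 2: where the patient lands.** No rule names this patient. SD is not PR or CR. Category 9 is scored as treatment failure under Section 13.5.2. Either way the patient is a non-responder for ORR.

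**Step 3: reproduce the design figures (Section 13.1).** Stop if 0 of 10; succeed if at least 3 of 20. With response rate p:

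- P(stop) = (1−p)^10
- P(success) = P(X1=1)·P(X2≥2) + P(X1=2)·P(X2≥1) + P(X1≥3), with X1 and X2 both Binomial(10, p)

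At p = 0.25: P(stop) = 0.0563; P(success) = 0.1877×0.7560 + 0.2816×0.9437 + 0.4744 = 0.8820. At p = 0.05: P(stop) = 0.5987; P(success) = 0.0686. These match the stated 5.6%, 88%, 60% and 6.9%.

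**Step 4: illustration.** Let q be the share of true responders who fall in the gap and have no other qualifying scan. The documents give no value; 5% to 30% is assumed. With a true rate of 25%, the counted rate is 0.25(1−q).

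| q | Counted rate | Power | Fall in power (points) | Stage-1 stop |
|---|---|---|---|---|
| 0 | 25.0% | 88.2% | – | 5.6% |
| 5% | 23.75% | 85.8% | 2.4 | 6.6% |
| 10% | 22.5% | 82.9% | 5.3 | 7.8% |
| 20% | 20.0% | 75.9% | 12.3 | 10.7% |
| 30% | 17.5% | 66.9% | 21.3 | 14.6% |

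At 25%, 20 patients give 0.25×20 = 5 expected responders, so these shares run from 0.05×5 = 0.25 to 0.30×5 = 1.5 patients per cohort.

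**Step 5: type I error after amending PR.** This depends on which wording the 5% unworthy rate refers to.

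- If 5% is the rate under the amended wording, the current wording gives a success probability of 6.1/5.3/4.0/2.8% at q = 5/10/20/30% (counted rate 0.05(1−q)), and the amendment returns it to 6.9%.
- If 5% is the rate under the current wording, the rate under the amended wording is 0.05/(1−q) = 5.26/5.56/6.25/7.14%. The Step 3 formula then gives 0.0775/0.0879/0.1149/0.1538, that is 7.7/8.8/11.5/15.4%.

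ALCL has no stated target rate, so nothing is computed there.

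**The case against.** Four counter-arguments have weight.

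*The PR condition applies only if the sites of disease were PET positive at baseline.* If involved marrow was PET-silent at baseline, not every site was PET positive, and a reader may hold that the condition is not triggered and PR is open. This stands: that case is ambiguous. The same reading is available for an involved spleen or liver that was PET-silent at baseline. It does not help where the marrow or organ was PET positive at baseline and has since cleared on PET.

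*The cited criteria may settle the case.* They may, but their content is not in the documents, and Section 11.1.1 points to the in-text definitions. What stands is that any new wording must be checked against them.

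*Nothing sends the patient to category 9.* This is correct. A reader might infer that the plan scores this patient as a treatment failure. The documents do not say so, the label of category 9 fits a fully assessed patient poorly, and an assessor might simply record PR. That different assessors could record different categories is itself the difficulty.

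*The effect is tiny and enrollment has closed.* The number is probably small, and the stage-1 figures describe accrual decisions that can no longer change. The success rules still have to be applied to the recorded responses, however, and a count of real cases would settle the size.

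**Conclusion.** The gap is real on the plan's own text and bears on the primary endpoint. It is definite where PET-positive disease has cleared on PET, shrinkage is at least 50%, and CR fails only on a palpable spleen/liver or on marrow that was PET positive at baseline and is still involved. It is ambiguous for disease that was PET-silent at baseline. It should be corrected, but it does not invalidate the design.

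The size is unknown. The power losses rest on assumed shares and are illustration only. A reader might infer from them that a cohort's verdict has been reversed, but the documents contain no count of affected patients and support no such statement. Nor can it be said without condition that amending PR leaves type I error at 6.9%: that holds only if the 5% unworthy rate is defined under the amended wording.

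A lesser point is that the opening and closing sentences of PD do not sit together, since any new lesion counts but baseline-positive sites must remain positive. Nor do they sit easily with the reference to recurrent or progressive disease in Section 11.1.3. This affects PFS and the duration endpoints, which are secondary and, under Section 13.4, descriptive unless otherwise noted.

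**What to change.** For endpoint classification only:

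1. Amend the PR sentence so that a patient who meets the size, no-growth, no-new-site and existing spleen/liver conditions, but not every CR criterion, is PR whether or not a site remains PET positive.
2. Make SD the remainder between PR and PD.
3. State whether Section 11.1.2.1 or the cited criteria govern, check the new wording against the cited criteria, and name the same criteria in Section 13.4.
4. Have central review apply this uniformly to all three cohorts. Section 11.1.5 describes only PET/CT scans being sent, so marrow and spleen/liver findings must be supplied as well.
5. Date the change, report the number of patients affected, and give ORR under the current and the amended wording.
6. Fix before the analysis which of the two drives each cohort decision.

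The PD sentences should be reconciled with each other and with Section 11.1.3. No PD rule is proposed here, because progression is also a criterion for stopping treatment (Section 5.3).

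The main cost is credibility. The change widens the responder wording after enrollment closed in October 2019, in an open single-arm study whose Principal Investigator and statistician have data access at all times (Section 12.1), so it can look data-driven. Steps 4 to 6 are the protection against that. Some cases may need re-reading, but only existing scans, biopsies and examinations are used. If no patient is affected, the two ORRs agree.

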5.4 Duration of Follow Up

Patients who discontinue treatment for reasons other than disease progression will be followed with CT scans at 6 and 12 months or until disease progression or next therapy for PFS and DOR endpoints. Follow-up after treatment discontinuation for progression, or after documented progression following discontinuation of therapy for reasons other than progression initially, will be by phone every 6 months for up to 1 year after the discontinuation of treatment for OS endpoints. Patients removed from study for unacceptable adverse event(s) will be followed until resolution or stabilization of the adverse event.

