11.1.3 Duration of Response

Duration of overall response: The duration of overall response is measured from the time measurement criteria are met for CR or PR (whichever is first recorded) until the first date that recurrent or progressive disease is objectively documented (taking as reference for progressive disease the smallest measurements recorded since the treatment started).

The duration of overall CR is measured from the time measurement criteria are first met for CR until the first date that progressive disease is objectively documented.

Duration of stable disease: Stable disease is measured from the start of the treatment until the criteria for progression are met, taking as reference the smallest measurements recorded since the treatment started, including the baseline measurements.

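### The PET sentence in the PD definition is tied to the baseline sites, so it conflicts with relapse after PET clearance and cannot be checked on the CT-only scans used for PFS and DOR

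*Combined protocol and SAP*

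**What the plan says.** Section 11.1.2.1 gives PD two limbs: "Any new lesion or an increase by" at least 50% of previously involved sites from nadir. It then lists what this covers, including a new lesion over 1.5 cm in any axis. The last sentence adds: "If the sites of disease were PET positive at baseline, they must remain PET positive". It does not say which limb it governs.

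Other provisions bear on it:

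- **CR (11.1.2.1).** For disease that was FDG-avid before therapy, "a mass of any size is permitted if PET negative". CR is therefore reached by baseline sites becoming PET negative.
- **PR (11.1.2.1).** For disease PET positive at baseline, "there must be at least one previously involved site that remains PET positive".
- **Governing standard (11.1).** "Response and progression will be evaluated in this study using the International Harmonization Project for lymphoma criteria". Section 11.1.1, however, has evaluable patients classified by the definitions that follow it in the protocol.
- **Follow-up imaging (5.4; section 10, footnotes i and j).** "Patients who discontinue treatment for reasons other than disease progression will be followed with CT scans at 6 and 12 months". These scans serve PFS and DOR, and no PET is scheduled with them.
- **Endpoints.** PFS ends at progression or death (11.1.4, 13.4). In 11.1.3, duration of overall response ends at recurrent or progressive disease, while duration of CR runs "until the first date that progressive disease is objectively documented". In 13.4, DOR ends at documented progression or death, and is censored at the last assessment before any new therapy.

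**The concern.** A PET condition in a PD rule would ordinarily qualify the lesion on which progression is called. Here it qualifies the sites that were positive at baseline and requires continuity. A metabolic CR breaks that continuity by definition, so the sentence bears hardest on the best responders.

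DOR uses responders only, and a cohort can succeed with three of them (13.1). One misdated relapse would then affect 1/3 of the DOR data. A relapse that is seen, not called PD, and then treated would be censored for DOR under 13.4, and scanning stops at next therapy under 5.4. Such censoring is informative, because it is triggered by the relapse itself.

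**Working it through.** **1. Apply the sentence to three cases, for disease PET positive at baseline.**

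| Case | Size and new-lesion criteria | PET sentence read literally | Result |
|---|---|---|---|
| A cleared baseline site regrows by at least 50% from nadir | Growth limb met | Site did not remain positive | PD blocked |
| Baseline sites cleared; new lesion over 1.5 cm elsewhere | New-lesion limb met | Baseline sites did not remain positive | The definition contradicts itself |
| Growth first seen on a 6- or 12-month CT | Growth limb met | PET status unknown | Condition cannot be checked |

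The first case is the clearest conflict. In the second, no other category fits if PD is refused: CR needs all disease to be gone, and both PR and SD exclude new sites. The third gap remains even if the sentence is confined to the growth limb.

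**2. Who reaches the CT-only scans.** On treatment, PET/CT is done every 8 weeks (11.1), and the off-treatment visit in section 10 includes FDG-PET/CT. Only the 6- and 12-month scans lack PET. Section 5.3 takes every patient off drug by May 31, 2020, which moves anyone still responding then into this follow-up.

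**3. Who reads the scans.** Section 11.1.5 assigns response rate and response duration to central review, but lets the local reading decide whether a patient stays on study. Two readers of the same sentence can therefore reach different PD dates.

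**4. Primary design.** In the MCL and DLBCL cohorts the rule is stop at 0/10 and succeed at 3 or more of 20, with 5% and 25% as the unworthy and worthy rates (13.1).

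- P(stop) = (1 − p)^10: 0.95^10 = 0.599 and 0.75^10 = 0.056 (stated 60% and 5.6%).
- P(success) = Σ over x = 1 to 10 of P(X = x) · P(Y ≥ 3 − x), with X and Y each binomial(10, p): 0.0686 at 5% and 0.882 at 25% (stated 6.9% and 88%).
- ALK+ ALCL, 3/10, exact 90% interval: 8.7% to 60.7% (stated 9-61%).

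All reproduce. The PD sentence enters none of these formulas.

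**5. Illustration for PFS and DOR.** The plan states no figure for either, and gives no CR rate, relapse pattern or post-relapse survival. Every input here is an assumption: a share c of 5-25% of a cohort clears on PET; median PFS m0 is 2-3 months if not cleared and m1 is 8-10 months if cleared; median survival after relapse s is 6-9 months; and a share q of 25-100% of cleared patients' relapses goes uncounted until death. Times are exponential.

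- Relapses counted: S(t) = (1 − c)·2^(−t/m0) + c·2^(−t/m1).
- Relapses uncounted: the affected patients' event time becomes relapse time plus post-relapse survival.

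Medians come from simulation with 200,000 patients per setting:

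| c | m0, m1, s (months) | q | Cohort median PFS | Median time to event, cleared patients |
|---|---|---|---|---|
| 5% | 2, 8, 6 | 25% | 2.10 → 2.11 | 8.06 → 10.17 |
| 10% | 2, 8, 6 | 50% | 2.22 → 2.28 | 8.00 → 12.26 |
| 25% | 3, 10, 9 | 100% | 3.85 → 4.57 | 9.98 → 23.00 |

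Check of the first starting value: 0.95·2^(−2.10/2) + 0.05·2^(−2.10/8) = 0.459 + 0.042 ≈ 0.50.

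The last column runs from treatment start and stands in for DOR. Censoring at next therapy and progression missed on CT-only scans were not modelled.

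**The case against.** The strongest reply is that the sentence naturally belongs to the growth limb. It speaks of baseline sites, and a new lesion is not one; "This includes the appearance of any new lesion(s") names new lesions as PD outright. A reading that leaves a relapsed patient in no category argues against itself, and section 11.1 names an external standard. Much of this stands. A reader might infer that a new-site relapse after clearance can never be PD, but the definition's own first limb says otherwise. It does not settle regrowth of a cleared site, and the general citation does not cure the wording, because 11.1.1 sends classification to the protocol's own definitions.

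A second reply is that relapse is covered elsewhere: 11.1.3 ends overall response duration at recurrence as well as progression. That is fair for that definition. Recurrence is absent from duration of CR in the same section and from DOR in 13.4.

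Third, a reader might infer that no progression first seen at 6 or 12 months can be declared. A new lesion on CT can still meet the first limb, so the gap at those scans is mainly in the growth limb.

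Fourth, a reader might infer that PFS and DOR are inflated as a matter of fact, or that three relapsing complete responders would leave median DOR unreached. Neither follows. The effect depends on how readers apply the sentence. Death is an event for PFS and for DOR in 13.4, and DOR time stops accruing at the last assessment before new therapy. Both endpoints are secondary and descriptive.

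**Conclusion.** The concern holds as a defect in a stated endpoint rule. The PET condition is placed on the wrong object, conflicts with the new-lesion limb, blocks PD on regrowth after PET clearance when read literally, and cannot be checked on the CT-only scans that feed PFS and DOR. If applied literally, the net direction is toward longer PFS and DOR, with DOR the more sensitive because it contains only responders.

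The size is not derivable from the documents. The 0.01 to 0.7 month shift in median PFS, and the larger shift in PET-cleared patients, rest entirely on assumed inputs and on the literal reading. Sample size, type I error, power and the go/no-go rule do not change. This deserves correction before PFS and DOR are analysed, but it ranks below a must-fix.

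**What to change.** For endpoint derivation:

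1. Reword the last sentence of the PD definition so that any PET condition applies to the new or enlarging lesion, and does not require baseline sites that cleared to have stayed PET positive.
2. State in 5.4 and 13.4 that, on CT-only follow-up scans, PD for PFS and DOR is derived from the size and new-lesion criteria already in 11.1.2.1.
3. Align the end event of DOR between 11.1.3 (recurrent or progressive disease) and 13.4 (documented progression or death).

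Progression is also a reason to stop treatment (5.3). Sections 5.3, 5.4, 10 (footnotes i and j), 11.1 to 11.1.2.1, 11.1.3 and 13.4 therefore have to be reconciled together. This point concerns how the endpoints are derived and does not propose a treatment-stopping rule.

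The cost is a few sentences of wording and possibly re-deriving PD dates from scans already taken. No patient or scan is added. PFS and DOR may look slightly less favourable.
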